6. 6-month change in the composite of inflammation and fibrosis, measured by the cT1 score, using *LiverMultiScan*
7. 6-month change in liver stiffness measurement (LSM) of fibrosis, assessed by vibration controlled transient elastography
8. 6-month changes in body weight (kg) and body mass index (BMI).

Exploratory Endpoints:

9. Changes in circulating biomarkers of aspirin target engagement
10. Changes in levels of pro- and anti-inflammatory lipid species and plasma metabolites, and changes in gut microbial composition and function, that may be impacted by aspirin therapy

Safety Endpoints:

Safety endpoints will be assessed according to the following schedule, and will be closely monitored by the IRB and by the Data Safety Monitoring Board (DSMB). Criteria for individual and/or study discontinuation based on safety assessments are outlined in detail below (see Safety Monitoring).

1. CBC: assessed at screening, baseline, and 6 months (and hematocrit additionally assessed at 3 months)
2. Pregnancy testing at all visits

III. SUBJECT SELECTION

A. Eligibility

Inclusion criteria:

1. Ages 18 to 65 years
2. NAFLD defined as confirmed hepatic steatosis (>5% intrahepatic triglycerides) by liver biopsy (within 12 months of screening) or by validated imaging modality (non-contrast CT scan, 1H-MRS, MRI-PDFF, ultrasound), in the absence of significant alcohol consumption (>2 drinks daily for women, >3 drinks daily for men) and other causes of hepatic steatosis. If relevant liver imaging (defined above) or liver biopsy has not been performed clinically within the prior 12 months before the screening date, liver ultrasound will be performed as part of the screening visit.

Exclusion criteria:

1. Other chronic liver disease, including viral hepatitis B or C infection, alpha-1 antitrypsin deficiency, Wilson's disease, hemochromatosis, autoimmune hepatitis, primary biliary cholangitis, primary sclerosing cholangitis, or HIV infection, as defined by medical record review or by patient self-report, and confirmed with the treating medical provider.
2. Alcohol intake greater than or equal to two drinks per day in women or three drinks per day in men.

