11. Recruitment through a list of research subjects who have previously been recruited by our study team and have agreed to recontact for future studies.
12. Recruitment through materials distributed to providers who care for NAFLD patients outside of the Partners System.
13. Recruitment through the Research Match (Vanderbilt Recruitment Tool)

Subjects who express interest will be pre-screened via a REDCap questionnaire or phone.

IV. SUBJECT RECRUITMENT

A. Trial Population

Subjects responding to the initial recruitment advertisements will undergo initial screening and if deemed potentially eligible for participation, they will be contacted by telephone and invited to participate in a screening visit. Based on a conservative assumption of 60% rate of either screening failure or subjects declining to participate in a research study, we expect to screen 200 adult subjects and enroll a total of 80 subjects with confirmed NAFLD without cirrhosis.

B. Consent

All subjects will receive the consent form for the study as well as the Human Subject's Bill of Rights. These documents will be read by the study subjects and also reviewed carefully by the study subject with a clinician on the research staff, prior to participating in the study. Any questions, concerns, or ambiguities will be appropriately clarified by the study clinician prior to the patient signing consent. Potential study subjects will sign informed consent and only then will they begin participation in the study. If new information is ascertained during the study, we will modify our consent and re-consent our patients accordingly.

C. Randomization

After baseline testing, 80 subjects who meet all eligibility criteria will be randomized to one of two treatments for 6 months: 1) low-dose aspirin (81mg per day), or 2) identical, blinded placebo pills.

Study Endpoints	Month 0	Month 6
Intrahepatic Lipids (1H-MRS)	✓	✓
Inflammation / Fibrosis (LiverMultiScan, Fibroscan)	✓	✓
Specialized Proresolving Mediators (SPMs)	✓	✓
Untargeted Eicosanoids, Inflammatory Markers	✓	✓
PNPLA3 rs738409 genotype	✓	

*All subjects will have NAFLD with fibrosis stage 0-3 (F0-3) confirmed by prior clinical liver biopsy or by validated imaging modality.

V. STUDY PROCEDURES:

A. Overview of Study Design.

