 - NAFLD Fibrosis Score will be calculated from standard labs and subject characteristics (age, BMI, blood glucose, platelet count and albumin).
 - Serum and Plasma will be collected for future measurement of lipids, bile acids, other metabolites including adipokines and inflammatory markers.
- Additional peripheral blood (serum, plasma, and whole blood) from which we will extract DNA and RNA. This will permit testing (among other things) for the *PNPLA3* rs738409 genotype, as this is an established NAFLD risk locus, and testing of *PNPLA3* is currently recommended in NAFLD/NASH clinical trials⁸.
- Stool samples that have been collected at home will be brought with the patient on the Baseline Visit. A collection kit provided during the Screening Visit will allow minimal contact with the stool and allow easy storage of the sample until the day of the Baseline Visit. If the patient forgets or is unable to complete the sample collection prior to their appointment, they may be given the materials to mail their sample to the study staff.
- MRI: 1H-MRS of the right and left hepatic lobe will be performed to quantify hepatic lipid content and other fat depots. LiverMultiscan sequences will also be performed for noninvasive analysis of hepatic inflammation and fibrosis. During the same MRI session,

MRI-PDFF will also be performed. MRI will be repeated at the 6-month visit (for a total of 2 MRI sessions per subject).

- Fibroscan to measure liver stiffness via transient elastography (ultrasound). Fibroscan will be repeated at the 6-month visit (for a total of 2 Fibroscans per subject).
- Standard bionutrition assessment by trained research nutritionist.
- Assessment of adherence (month 6 visit) by returned pill count and by self-report.
- Three validated questionnaires will be administered to subjects:
 - The Paffenbarger Physical Activity questionnaire
 - The SF-36 health survey questionnaire
 - The semi-quantitative Food Frequency Questionnaire (FFQ)

Total Blood Drawn: Total blood volume from the participant is below 200ml for this Baseline Visit and for the Month 6 visit. As this is below 300ml over at least 6 hours, this does not result in added risk. Normal blood donation volume is 450-500ml.

2. Follow-up 3-month visit: (n=80)

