³², according to published criteria^{33, 34}. [name] together with Co-Investigator [name] have shown excellent reproducibility of this method for quantifying eicosanoid derivatives, including SPMs and other circulating lipid mediator species^{32, 34}, with a lower limit of detection of ~0.1pg³⁴. Notably, this method will also permit measure of SPM precursors (e.g. erythrocyte docosahexaenoic acid [DHA], eicosapentaenoic acid [EPA]), which also reflect dietary intake, aspirin use and hepatic DHA/EPA^{35, 36}, and which may impact hepatic steatosis³⁷.

Stool Metagenomics: Stool samples will be collected at home on two instances (before the Baseline Visit and Before Visit #4). A collection kit will allow minimal contact with the stool and allow easy storage of the sample until the day of the study visit. If the patient forgets or is unable to complete the sample collection prior to their appointment, they may be given the materials to mail their sample to the study staff at a later date. Stool samples will be collected on a spoon and placed into two tubes. The tubes will be included in stool collection kit and will contain 95% ethanol for both future DNA/RNA extractions and metabolomic analysis. Upon receiving the samples, the stool in the first tube will be centrifuged and separated from the fixative. Then, both stool samples will be stored at -80°C in the lab of [name] and [name].

Genotyping

Genomic DNA samples will be used for the identification and/or genotyping of polymorphisms that may predict the pathogenesis and progression of NAFLD. Additionally, polymorphisms in any one of many genes, including those encoding drug receptors, drug transporters, and cell signaling pathways, can be important determinants of clinical response. An advantage of developing a DNA-based diagnostic test as a clinical biomarker is that only a small sample of tissue (i.e. blood from a finger prick or buccal cells) is required for genotyping of a large number of polymorphisms. DNA-based diagnostic assays also provide a clinician the ability to perform high-throughput and accurate diagnostic tests for a reasonable cost.

Transcriptional Profiling

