To ensure data entry accuracy, peer review of source documentation and case report forms in REDCap will be completed following MGB Study Data Management and Quality Assurance Plan Guidelines. Research coordinators will exchange subject files and review informed consents, case report forms, and adverse event logs for accuracy and completeness. Additionally, eCRFs in REDCap will be reviewed for accuracy and completeness using source data verification.

C. Statistical Analysis and Power

Data Analysis Plan:

This statistical analysis plan will be finalized before database lock. Baseline data between groups will be compared using chi-squared test or Fisher's exact test for categorical variables, and using ANOVA for continuous variables, with any non-normally distributed data log-transformed prior to analysis. If significant baseline group imbalance is detected on any particular variable, that variable will be included as a covariate in the analyses.

Absolute and relative changes in continuous outcomes between treatment groups will be calculated using analysis of covariance (ANCOVA), with treatment group at randomization included as a fixed effect, and the baseline value of the relevant outcome included as a covariate. Logistic regression will be used for binary outcomes (i.e., achievement of $\geq 30\%$ relative HFF reduction). For the primary analysis, all study endpoints will be analyzed using an intention-to-treat approach, using data from all randomly assigned participants in the full analysis set. The primary analysis will assume that missing data were missing at random³⁸, and data augmentation for missing observations will be conducted via multiple imputation, using all available non-missing data of the outcome measurement from the same treatment arm.

We will also utilize data from all participants who adhere to therapy as assigned and complete the final, 6-month visit for study outcomes (i.e., the per protocol analysis set).

We will conduct the following subgroup and sensitivity analyses for the primary and key secondary endpoints:

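### A mailed-in baseline stool sample need not precede the first dose, so the plan permits an on-treatment baseline for the stool part of exploratory endpoint 10

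*Combined protocol and SAP*

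**What the plan says.** The default is a sample taken before the visit. Section V.A (Baseline and 6-month visit) states: "Stool samples that have been collected at home will be brought with the patient on the Baseline Visit". Section V.C (Stool Metagenomics) plans two home collections, one ahead of the Baseline Visit and one ahead of Visit #4.

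Both sections then allow an exception. Its trigger is worded "If the patient forgets or is unable to complete the sample collection prior to their appointment", so it is the collection itself, and not only the postage, that falls after the visit. For these participants Section V.A says "they may be given the materials to mail their sample to the study staff", and Section V.C says "they may be given the materials to mail their sample to the study staff at a later date". The Section V.C wording follows directly on the two planned collections and so covers both.

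On sequence, Section IV.C (Randomization) says "After baseline testing, 80 subjects who meet all eligibility criteria will be randomized to one of two treatments for 6 months". The table there labels the two measurement times Month 0 and Month 6. No first-dose date appears anywhere, and Section V.A describes no dispensing visit between the Baseline Visit and the 3-month visit.

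The endpoint concerned is item 10 of the Exploratory Endpoints in Section II, which includes "changes in gut microbial composition and function, that may be impacted by aspirin therapy". For continuous outcomes, Section VI.C plans ANCOVA with "the baseline value of the relevant outcome included as a covariate".

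**The concern.** A baseline value should be free of treatment. Here a participant can leave the Baseline Visit without having given stool, be randomized, start capsules, and collect the baseline sample some days or weeks later without departing from the protocol. In the aspirin arm that sample may already contain part of the effect that endpoint 10 is meant to detect. In the placebo arm it cannot. Neither randomization nor blinding removes this asymmetry, and adjusting for such a value means adjusting for a post-treatment variable. If the early effect runs in the same direction as the 6-month effect, the estimated arm difference shrinks toward zero.

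The problem would not show in the data unless collection and dosing dates are held together. The protocol asks for neither a stool collection date nor a rule for late samples, and the analysis plan does not define baseline as the last value before dosing. What is at stake is a missed or diluted microbiome signal, not the trial's main result.

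**Working it through.** **Plan's own figure.** There is none for the microbiome endpoint. The sample size calculation in Section VI.C concerns liver fat by 1H-MRS only and plays no part here.

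**Does the text permit an on-treatment baseline?**

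1. The exception applies when collection has not happened before the appointment, so collection follows the visit.
2. Neither statement of the exception sets a latest date or mentions the first dose.
3. Randomization follows baseline testing, but nothing says that study drug waits for an outstanding stool sample.
4. Baseline is Month 0 and the next described visit is month 3, so starting drug at or soon after the Baseline Visit is the natural reading, though it is not stated.

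An on-treatment baseline is therefore allowed. Nothing shows that it must occur.

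**Size. All inputs are assumptions; the documents give none.**

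- f = share of aspirin-arm baseline samples taken after the first dose: 20%.
- s = share of the 6-month effect already present in those samples: 50% to 100%. The upper end is extreme.
- b = ANCOVA slope of the month-6 value on baseline: 0.3 to 0.7.
- D = true arm difference at month 6.

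The mean aspirin baseline moves by f × s × D. The placebo baseline does not move.

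*Raw change score.* Estimate = D − f × s × D, so the loss is f × s:
- s = 50%: 0.2 × 0.5 = 10%
- s = 100%: 0.2 × 1.0 = 20%

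*Planned ANCOVA.* The baseline difference is multiplied by b before it is subtracted, so the loss is about b × f × s:

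| b | s = 50% | s = 100% |
|---|---|---|
| 0.3 | 3% | 6% |
| 0.5 | 5% | 10% |
| 0.7 | 7% | 14% |

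*Late month-6 samples.* If 20% of aspirin participants also sent month-6 stool with half the effect gone, the further loss is 0.2 × 0.5 = 10%. It is not scaled by b, because it sits in the outcome. The totals become 20% to 30% for a change score and 13% to 24% under ANCOVA.

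*Power.* Take a hypothetical microbiome measure with 80% power when undiluted. With a fraction k of the effect retained, and the variance unchanged, power is about Φ((1.960 + 0.842) × k − 1.960):
- ANCOVA, baseline contamination only: k = 0.97 gives Φ(0.758) = 78%; k = 0.86 gives Φ(0.450) = 67%.
- Change score, baseline contamination only: k = 0.90 gives 71%; k = 0.80 gives 61%.

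**The case against.** The strongest reply is that Section IV.C places randomization after baseline testing and Section V.A lists stool among the baseline assessments. On that reading an outstanding sample is unfinished baseline testing, and drug would not start without it. This is a possible reading, and it is why an on-treatment baseline can only be called permitted. It does not close the gap, because the mail-in exception is not tied to that sequence and no sentence withholds drug until the stool is collected.

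Second, a reader might infer a loss of 10% to 20%. That is the change-score figure. Section VI.C plans ANCOVA, under which the same inputs give about 3% to 14%. This objection stands.

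Third, the default is sound. The kit is handed out at screening, up to 16 weeks before baseline, and mail-in is only for those who forget or cannot comply. The change log also records updated kit instructions in Version 6. Their content is not shown, so collection dates may already be recorded. This limits how often the problem would arise, but the log mentions no timing rule and reports no change to the analysis plan.

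Fourth, it is tempting to conclude that month-6 stool collected after the last dose should be dropped. The documents do not support that. Section VI.C analyses all endpoints by intention to treat, and the Early Termination Visit in Section V.A asks participants who leave early, after at least 11 weeks on study medication, for all final-visit assessments. Dropping off-drug samples would exclude people on a post-randomization event. This objection stands.

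Finally, the endpoint is exploratory, with no power calculation or multiplicity control. That bounds the importance of the point, but it is no reason to leave open a gap that costs so little to close.

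**Conclusion.** The concern holds in limited form. The mail-in exception has no deadline and no link to the first dose, so a stool sample taken on treatment can serve as baseline for the stool part of exploratory endpoint 10. A reader might infer that this will happen, or that the trial's main results are affected. The documents support neither: they give no first-dose date and no frequency of late samples, and no primary, key secondary or safety endpoint uses stool.

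Under the planned ANCOVA the dilution from baseline contamination is about 3% to 14%. This rests on assumed values of f, s and b, on the Section VI.C model being applied to the microbiome measures, and on early and 6-month effects having the same direction. A modest correction is warranted, because the bias is directional and cheap to prevent.

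**What to change.** - Keep the mail-in option, but require a mailed baseline stool to be collected before the first dose of study drug.
- Record the stool collection date and the first and last dose dates.
- Store a baseline stool collected after the first dose, but do not use it as the baseline value; treat baseline as missing.
- Keep month-6 stool collected after the last dose in the intention-to-treat analysis, flag it, and repeat the analysis without flagged samples as a sensitivity analysis.
- Reconcile the visit numbers. Section V.C (Additional Blood Samples) calls the Baseline Visit Visit 1, while the second stool sample is tied to an undefined Visit #4.

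The cost is a few sentences, date fields on the kit label and case report form, and one analysis rule. The rule can still be applied after collection if the dates exist. The downside is the loss of a few baseline stool values, which a reminder call before the Baseline Visit would limit.

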It has been recommended by subspecialty societies, including the American Association for the Study of Liver Disease (AASLD), that changes in liver fat content as quantified by magnetic resonance spectroscopy (MRS) or MRI proton density fat fraction (MRI-PDFF), can serve as an appropriate and clinically relevant primary outcome in early, phase 1 and 2 clinical trials of novel NAFLD therapeutics. Specifically, recent advances in MR-based imaging techniques now permit very accurate and validated means of quantifying intrahepatic lipids, via MRS and MRI-PDFF. Results of intrahepatic lipids (%) by MRS correlate closely with biochemical and histological assessment of liver triglyceride content, with an area under the receiver operating characteristic curve that exceeds 90%. Moreover, MRS measures global hepatic fat content across the entire liver (rather than from a small sample, from a liver biopsy), which is relevant as lipid content may be heterogeneous and thus liver biopsy could result in sampling error. Collectively, this robust prior evidence demonstrates that MRS (and MRI-PDFF) are robust and accurate means of quantifying steatosis for the primary endpoint assessment, in early-phase NAFLD interventional trials. In addition to these established MRI endpoints, the present study also includes an optional enrollment and month 6 liver biopsy, as part of the optional biopsy sub-study, but liver biopsy is not required for the main study.

II. SPECIFIC OBJECTIVES & ENDPOINTS

We will conduct a randomized, placebo-controlled trial to assess the feasibility and efficacy of aspirin for reducing liver fat, inflammation and fibrosis, in 80 adults aged 18-65 with established nonalcoholic fatty liver disease (NAFLD), confirmed by validated imaging modalities or by a clinical liver biopsy within 12 months of the screening visit.

Primary Efficacy Endpoint: 6-month absolute difference in % hepatic fat fraction (HFF), measured by 1H-MRS.

Key Secondary Endpoints:

1. Relative 6-month percentage change in HFF %, by 1H-MRS.
2. Proportion of patients with 30 percentage point or greater relative reduction in HFF, by 1H-MRS.
3. Absolute change in liver fat %, as measured by MRI-PDFF.
4. Relative percentage change in liver fat %, as measured by MRI-PDFF.

Non-Key Secondary Endpoints:

5. 6-month change in alanine aminotransferase (ALT) and aspartate aminotransferase (AST).

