To address potential confounding due to meaningful weight loss between baseline and month 6, we will exclude any participant who loses $\geq 3\%$ body weight during the 6-month study period. We will construct separate, multivariable-adjusted regression models accounting for *a priori* defined clinical confounders, including age, sex, race/ethnicity, type 2 diabetes status at baseline, fasting insulin level at baseline, body weight and visceral adipose tissue (VAT) volume, as previously recommended for NAFLD clinical trials⁸. We will also repeat the analyses with missing data for primary and key secondary endpoints considered as nonresponses, by carrying forward the baseline values. We will also conduct subgroup analyses for the endpoints of

absolute change in HFF by MRS (primary endpoint) and relative HFF change by MRS (key secondary endpoint) in participants with significant, stage 2-3 fibrosis at baseline.

Sample Size, Statistical Power & Multiplicity Testing:

We anticipate a conservative drop-out rate of approximately 15%, thus we estimate an effective sample size of 68 patients. Based on prior studies of a dietary intervention for hepatic steatosis (Ryan et al.³⁹), and data from a meta-analysis of oral omega-3 supplementation and hepatic steatosis (Parker et al.⁴⁰) we expect an effect size of 3% with the standard deviation of the change in liver fat of 2.45, by ¹H-MRS. Applying these estimates, the probability is >90% that the study will detect a treatment difference at a two-sided 0.05 significance level⁴¹. The Holm procedure to control for multiple testing will be applied to the 4 key secondary outcomes, as follows: P=0.0125 for relative change in HFF by MRS, P=0.0167 for proportion achieving ≥30 percentage point reduction in HFF by MRS, P=0.025 for absolute change in HFF by MRI-PDFF, and P=0.05 for relative change in hepatic fat by MRI-PDFF. For the other non-key secondary outcomes no multiplicity adjustments will be employed. For exploratory outcomes, no multiplicity adjustments will be used.

Definitions of Analysis Sets:

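### The SAP names no baseline covariate for the logistic model of the ≥30% HFF responder endpoint; prespecifying baseline HFF would be a cheap gain in efficiency

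*Combined protocol and SAP*

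**What the plan says.** Section VI.C, Data Analysis Plan, gives continuous outcomes an ANCOVA "with treatment group at randomization included as a fixed effect, and the baseline value of the relevant outcome included as a covariate". The next sentence begins "Logistic regression will be used for binary outcomes", cites the ≥30% relative HFF reduction as the example, and gives no terms for the model.

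Two other places bear on covariates:

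- The same section has a general rule: "If significant baseline group imbalance is detected on any particular variable, that variable will be included as a covariate in the analyses". It is not limited to continuous outcomes, and it states no significance level.
- The multivariable sensitivity models adjust for "age, sex, race/ethnicity, type 2 diabetes status at baseline, fasting insulin level at baseline, body weight and visceral adipose tissue (VAT) volume". Baseline HFF is not on that list.

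Section II lists the endpoint as key secondary number 2: "Proportion of patients with 30 percentage point or greater relative reduction in HFF, by 1H-MRS". The multiplicity paragraph of Section VI.C says "The Holm procedure to control for multiple testing will be applied to the 4 key secondary outcomes" and lists "P=0.0167 for proportion achieving ≥30 percentage point reduction in HFF by MRS". I read the endpoint as a relative reduction of at least 30%, as in the Data Analysis Plan. The percentage-point wording elsewhere is a separate matter to reconcile.

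**The concern.** The plan states its treatment effect in absolute points of liver fat, but the responder endpoint is a relative fall. If a patient's absolute change does not depend on where he or she started, the chance of response depends strongly on baseline HFF: a 30% fall is 0.30 × 6 = 1.8 points from a baseline of 6%, and 0.30 × 20 = 6 points from a baseline of 20%. Baseline HFF is then a strong predictor of response, and it is scheduled to be measured in every subject.

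Two things are at stake. The first is power on one of the four endpoints under multiplicity control. With about 34 patients per arm, an ordinary chance difference in baseline HFF moves the responder rates. The second is prespecification: with no terms listed, an adjusted and an unadjusted test are both open after the data are seen, and the imbalance rule lets a baseline test choose between them.

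**Working it through.** **Inputs from Section VI.C:** 80 randomised, 15% drop-out, effect 3 points, SD of change 2.45, two-sided alpha 0.05 for the primary endpoint, 0.0167 listed for the responder endpoint. **Assumed, because the documents do not give them:** 1:1 allocation, the distribution of baseline HFF, the responder rates, how change relates to baseline, and the significance level of the imbalance rule.

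**1. The plan's own figures.** 80 × 0.85 = 68, or 34 per arm. The standard error of the difference is 2.45 × √(2/34) = 0.594; 3/0.594 = 5.05; power = Φ(5.05 − 1.96) = 99.9%. The stated power above 90% is met. The Holm steps 0.05/4, 0.05/3, 0.05/2 and 0.05/1 give 0.0125, 0.0167, 0.025 and 0.05, as listed. The plan states no power for the responder endpoint.

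**2. Why baseline may or may not matter.** Take the mean change on placebo as zero.

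- *Absolute change independent of baseline b.* P(response) is Φ(−0.3b/2.45) on placebo and Φ((3 − 0.3b)/2.45) on aspirin. At b = 6 this gives Φ(−0.73) = 23% and Φ(0.49) = 69%. At b = 20 it gives Φ(−2.45) = 0.7% and Φ(−1.22) = 11%.
- *Change proportional to baseline.* The relative change has the same distribution at every baseline, so baseline does not predict response.

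**3. Power at alpha 0.0167, 34 per arm.** Likelihood-ratio test for treatment in logistic regression, 6,000 simulated trials per row, without and with baseline HFF:

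| Assumed baseline mean (SD), % | Change model | Unadjusted | Adjusted | Gain, points |
|---|---|---|---|---|
| 12 (5) | independent of baseline | 77.7% | 84.0% | +6.3 |
| 15 (6) | independent of baseline | 64.6% | 74.5% | +9.9 |
| 18 (8) | independent of baseline | 49.6% | 62.7% | +13.1 |
| 12 (5) | proportional | 85.6% | 85.8% | +0.2 |
| 15 (6) | proportional | 71.1% | 73.7% | +2.6 |
| 18 (8) | proportional | 57.9% | 56.1% | −1.8 |

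Other simulations with change independent of baseline gave 84% to 89% (mean 10, SD 5) and 66% to 75% (mean 15, SD 7). The smallest gain seen in that case was 4 points (86% to 90%).

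**4. The same question without a change model.** With assumed responder rates of 15% v 40% or 20% v 50%, the gain at 34 per arm depends on the odds ratio (OR) of response per SD of baseline HFF: about 1 to 3 points for an OR up to 1.5, 5 to 6 points at an OR of 2, and 9 to 11 points at an OR of 3.

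**5. Does the imbalance rule cover this?** At an assumed 5% level it fires in about 5% of randomised trials, half of them (2.5%) in the direction of higher baseline on aspirin. Take the fifth of trials in which aspirin's mean log baseline is highest relative to placebo's. The rule catches about 2.5/20 = 12.5% of these and leaves the other 87.5% alone. With change independent of baseline, unadjusted power in that fifth was 66% (mean 10, SD 5) and 48% (mean 15, SD 7), and adjusted power was 86% and 77%. Each figure rests on about 600 trials, so its standard error is about 2 points.

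**6. Type I error.** With 20% responders in both arms, rejection was 1.7–2.1% unadjusted and 1.8–2.4% adjusted, against a nominal 1.67%. With fewer responders (about 7% on placebo, mean 15, SD 7), it was 3.7% in both models. The excess comes from the likelihood-ratio test with sparse events and not from adjustment. With a Firth penalised fit that includes baseline, null rejection was 1.9% (mean 10, SD 5) and 0.7% (mean 15, SD 7). Power was 86% and 71%, against 83% and 63% for Firth without baseline.

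**The case against.** A reader might infer that the SAP prescribes an unadjusted responder analysis. It does not. The sentence lists no terms at all, not even treatment, so the text supports only that the covariates are unstated. The SAP was also to be finalised before database lock, which would have been the place to add them, though the change log records no SAP change after the trial began.

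A reader might also infer that chance imbalance in baseline HFF would go uncorrected. That is too strong: the imbalance rule applies to the analyses in general, so a significant difference in HFF would bring it into the logistic model. What stands is that the rule leaves most imbalance alone and is driven by the data.

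Third, a reader might take a loss of power as given. The endpoint is already scaled to baseline. If the change is proportional to baseline, adjustment gains about nothing, and the documents say nothing on how change relates to baseline HFF. The power figures in the table also come from a test that somewhat exceeds its nominal level when responders are few, so they show direction and rough size only.

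Finally, an unadjusted comparison is valid under randomisation and estimates a marginal effect. The primary endpoint and the other three key secondaries are continuous and already get baseline-adjusted ANCOVA. All of this stands, and it limits the point to one of efficiency and prespecification.

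**Conclusion.** The point holds as a gap in prespecification with a cheap remedy. Baseline adjustment is fixed in advance for every continuous outcome and unstated for the one binary key secondary, where baseline HFF would enter only if a baseline test happened to be significant.

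The expected gain is about 4 to 13 points of power if absolute change does not depend on baseline, and −2 to +3 points if change is proportional to baseline. These ranges assume 1:1 allocation, 34 evaluable patients per arm, the plan's effect and SD, and baseline distributions that the documents do not give. Under a penalised fit, which keeps the level at or near nominal, the gain with change independent of baseline was 3 points (83% to 86%) and 8 points (63% to 71%). Adjustment did not materially change the Type I error. The primary analysis is not affected.

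**What to change.** Before unblinding, add to the Data Analysis Plan that the logistic model for the ≥30% relative HFF reduction:

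- contains treatment and baseline HFF on the log scale, whatever the baseline comparison shows;
- is fitted by penalised (Firth) likelihood, because placebo responders may be few;
- is reported with a standardised risk difference and its confidence interval beside the odds ratio.

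No new data are needed. The text is short, but it should also say how the variance of the risk difference is obtained and how results are pooled over the multiple imputations. The one real downside is that the odds ratio becomes conditional on baseline HFF; the standardised risk difference supplies the marginal effect. If the team prefers an unadjusted model, stating that in advance would still close the open choice, at the possible cost in power shown above.
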